Research Protocol

Title: Ocular Sarcoidosis Open Label Trial of ACTHAR Gel

Principal Investigator: [name], DO

NCT Number: 02725177

Document Date: 05/14/2018

Investigator initiated study (IIS) Form

Principal Investigator: [name], DO

Institution and Department: Cleveland Clinic Respiratory Institute

Contact information: [name], DO
[name]
[name]
[name]

Date: May 14, 2018
Amendment 4

1. Title of Study:

Ocular Sarcoidosis Open Label Trial of ACTHAR Gel

2. Hypothesis:

Treatment with ACTHAR Gel will result in a reduction of ocular inflammation in patients with active ocular sarcoidosis that requires systemic immunosuppressant therapy

3. Rationale for the study:

The initial treatment of ocular sarcoidosis usually relies on a combination of topical glucocorticoids and oral glucocorticoids, both of which are associated with significant ocular and systemic toxicities. Steroid-sparing therapies are limited by variable and unpredictable efficacy, prolonged time until clinical response, medication intolerance, and difficulties obtaining payor approval. As a result, it is not uncommon that treating physicians must choose between excessive glucocorticoid toxicity versus poor control of ocular inflammation. Ongoing ocular inflammation, in turn, leads to eventual visual loss and occasionally blindness.

There is a need for a more reliable, expeditious therapy that can be used as an alternative to glucocorticoids in sarcoidosis uveitis. Adrenocorticotrophic hormone, through activation of melanocortin receptors on leukocytes, can dampen immune responses through non-glucocorticoid dependent mechanisms. The proposed study will aim to define whether there is effectiveness for ACTHAR gel in these patients, delineate an effect dosing regimen, and provide information about the safety of this approach for moderate to severe ocular sarcoidosis.

ACTHAR is a 39-amino acid peptide natural form of adrenocorticotropin hormone (ACTH) that was initially approved in 1952 by the FDA. It has since been approved for 19 indications including respiratory sarcoidosis, multiple sclerosis, and infantile spasms.

4. Patient Population and Estimated Sample Size:

Patients with sarcoidosis (as defined by ATS/ERS/WASOG criteria) who have moderate to severe ocular sarcoidosis, defined as:

1. Any posterior, intermediate or panuveitis of sufficient severity to warrant therapy, in the opinion of the treating physician –OR—

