2. Anterior uveitis requiring 4 or more daily applications of topical corticosteroids to maintain control of inflammation.

We propose to enroll patients, at the Cleveland Clinic, until at least 20 patients have successfully completed 4 weeks of therapy in this open label trial in order to determine effect size, speed of response and tolerability. In the event the Cleveland Clinic is unsuccessful in recruiting a sufficient number of subjects additional sites may be added as needed.

Statistical Analysis: The proof of concept patient population will consist of patients with ocular sarcoidosis. The definition of condition improvement is such that the patients will be classified under any of the following:

- a) Improved visual acuity (by at least one grade)
- b) Resolution of intraocular inflammation (no more than trace cells)
- c) Tapering of ocular or oral steroids by at least 50%
- d) Reduction of cystoid macular edema (graded by the ophthalmologist)
- e) No worsening of any of the above

Given these conditions, the acceptance of a composite endpoint and an assumption that only 20% of those with intraocular sarcoidosis will spontaneously remit or improve on the composite endpoint in the time-frame of the study, inclusion of 20 patients confers an 87% power to identify a 50% response rate from the medication at a two-sided alpha error rate of 0.05

The Cleveland Clinic will oversee the study, and maintain responsibility for collection of the case report forms and analysis of the data.

Study Design:

Inclusion/Exclusion Criteria

Inclusion Criteria

- Patient with sarcoidosis as defined by ATS/ERS/WASOG guidelines
- Any posterior, intermediate or panuveitis of sufficient severity to warrant therapy, in the opinion of the treating physician --OR-- Anterior uveitis requiring 4 or more daily applications of topical corticosteroids to maintain control of inflammation, or uncontrolled with topical therapy
- Persistent disease activity (active uveitis) at the time of screening

Exclusion criteria

- Other cause for ocular inflammation
- Uncontrolled diabetes, hypertension, or other contra-indication to increased dosage of glucocorticoids

- Recent (less than 4 weeks) intra-ocular or intra-orbital steroid injection
- Escalation of immunosuppressive medications between screening and initiation of the study medication
- Severe extra-ocular sarcoidosis likely to require additional therapy (in the opinion of the investigator)

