Visual acuity (Snellen)	X	X	X	X	X	X	X	X	X	X	X
Retinal angiography		X		X			X		X		X
Optical coherence tomography		X		X			X		X		X
Assess organ involvement	X	X		X			X	X	X	X	X
QOL instruments (FAS, KSHQ, SHQO)		X		X		X	X		X		X
Toxicity assessment			X	X	X	X	X	X	X	X	X
Medication list	X	X	X	X	X	X	X	X	X	X	X
Dispense medication		X		X		X	X	X	X	X	
Inflammatory biomarkers (serum draw for freezing)		X		X		X	X	X	X		X
Patient stipend	X	X	X	X	X	X	X	X	X	X	X

Protocol for treatment failure

[figure not shown]
- Treatment failure will be defined as any of:
 - Two step increase from baseline in SUN activity (anterior chamber) grade on two consecutive readings, or increase from Grade 3 to Grade 4
 - Failure to demonstrate improvement by 12 weeks in subjects with baseline SUN Grade ≥ 2
 - Failure to demonstrate any improvement by week 24 in SUN Grade 0-1+
 - Significant worsening of vitritis, retinal vasculitis, or macular edema associated with reduction of visual acuity
 - No improvement of vitritis, retinal vasculitis, or macular edema by week 12 in subjects with more than trace vitreous cells
- In the event of worsening inflammation during prednisone tapering, the dose of prednisone will be increased to the last dose level for an additional 4 weeks, prior to resumption of the tapering schedule
- In the event of treatment failure prior to the prednisone tapering phase, or in the event that the subject requires a second prednisone escalation, the subject will be dropped from the trial, and management of uveitis will be at the discretion of the treating physician.

Criteria for drug interruption or discontinuation

- Uncontrolled hyperglycemia requiring hospitalization, leading to other complications, or unable to be controlled with anti-diabetic medications
- Vision-threatening elevation of intraocular pressure unable to manage with topical anti-glaucoma therapy
- Infections requiring hospitalization (medication may be resumed after the infection is

resolved)

- Other severe medical complications deemed to be likely associated with study medication in the opinion of the investigator

5. Primary end-point:

(Measured at 24 weeks):

Proportion of patients meeting the composite of improvement of any one of the following variables, with no worsening of any single one, and no need for additional sarcoidosis therapies:

- visual acuity
- resolution of intraocular inflammation
- tapering of ocular or oral steroids by at least 50%
- reduction of cystoid macular edema

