6. Secondary end-points:

- Proportion of patients meeting the primary endpoint at 4, 8 and 12 weeks
- Toxicity (including intraocular pressure)

- Durability of effectiveness (out to 48 weeks)
- Quality of life
- Inflammatory biomarkers
- Extra-ocular organ activity

7. Estimated time line (including contracting, IRB approval, study initiation, enrollment, study completion and submission of publication):

Thirty-six months, including six months to complete contracting and protocol development, 24 months for patient recruitment and study, and six months for data analysis and manuscript submission

8. Adverse Events and Data Monitoring

The risks of ACTHAR include and are not limited to those seen with glucocorticoid use. Acthar Gel causes the release of endogenous cortisol from the adrenal gland. Therefore all the adverse effects known to occur with elevated cortisol may occur with Acthar Gel administration as well. Common adverse reactions include fluid retention, alteration in glucose tolerance, elevation in blood pressure, behavioral and mood changes, increased appetite and weight gain.

Substantial side effects related to ACTHAR gel could include infection requiring parenteral antibiotics or any opportunistic infection; diabetes that cannot be controlled with conventional therapy; fluid retention that cannot be controlled with conventional diuretics; mood or personality changes deemed in the opinion of the investigator to require dose reduction.

The subject will undergo a focused history and physical examination at nine study assessment dates. The appropriate laboratory and ocular studies will be obtained as per the timeline. The study coordinator will contact patients by phone during the induction period. Adverse events that take place during the testing or afterwards will be recorded along with the patient's data and will be reported directly to the IRB by the PI. A data monitor will be assigned to the study.

All tests are routinely performed here at the Cleveland Clinic. The risks of each procedure are minimal.

9. Ethical considerations

Recruitment

We propose to enroll patients, at the Cleveland Clinic, until at least 20 patients have successfully completed 4 weeks of therapy in this open label trial in order to determine effect size, speed of response and tolerability. In the event the Cleveland Clinic is unsuccessful in recruiting a sufficient number of subjects additional sites may be added as needed. These sites may include

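### A steroid taper of at least 50% is enough on its own for response, so a positive primary result need not show reduced ocular inflammation, and treatment failures are not tied to non-response

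*Combined protocol and SAP*

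**What the plan says.** Section 2 states the hypothesis: "Treatment with ACTHAR Gel will result in a reduction of ocular inflammation".

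Section 5 defines the primary endpoint ("Measured at 24 weeks") as the proportion of patients with "improvement of any one of the following variables, with no worsening of any single one, and no need for additional sarcoidosis therapies". The four variables are visual acuity, resolution of intraocular inflammation, reduction of cystoid macular edema, and "tapering of ocular or oral steroids by at least 50" percent. Any one suffices.

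Under Protocol for treatment failure, the text refers to a prednisone tapering phase. If inflammation worsens during it, "the dose of prednisone will be increased to the last dose level for an additional 4 weeks, prior to resumption of the tapering schedule".

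The Statistical Analysis paragraph of Section 4 assumes that "only 20% of those with intraocular sarcoidosis will spontaneously remit or improve on the composite endpoint", and states 87% power with 20 patients to detect a 50% response rate at two-sided 0.05. The same paragraph holds the protocol's only definition of improvement, and that list includes the 50% steroid taper.

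**The concern.** Steroid dose is partly a trial procedure and also a scored outcome. The no-worsening condition asks for stability, so under Section 5 a patient whose inflammation is unchanged but whose steroid dose has been halved can be a responder. The trial is open label with no control group described, so nothing in the design separates a directed reduction in background treatment from an effect of the drug.

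Section 8 adds that "Acthar Gel causes the release of endogenous cortisol from the adrenal gland". A lower prednisone dose therefore need not mean lower total glucocorticoid exposure.

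At stake is what a positive result means. It could rest to an unknown extent on taper-only responders, and to that extent would not support the hypothesis in Section 2.

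**Working it through.** **1. The plan's own figure.** Inputs from Section 4: n = 20, null rate 0.20, alternative 0.50, two-sided alpha 0.05. No test is named.

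- Normal approximation, with the null variance under the null and the alternative variance under the alternative: z = [√20 × (0.50 − 0.20) − 1.96 × √(0.20 × 0.80)] / √(0.50 × 0.50) = (1.342 − 0.784) / 0.5 = 1.115, so power is 0.868.
- Exact binomial, declaring success at 8 or more of 20: power 0.868, upper-tail error 0.032.

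Both reproduce the stated 87%. A stricter exact rule that holds the upper tail at 0.025 needs 9 or more of 20, with error 0.010 and power 0.748. Both cuts are carried forward.

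**2. Do other rules close the taper-only route?**

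| Rule | Place | Effect on scoring |
|---|---|---|
| Study drug stopped if no improvement after 4 weeks | Study Procedures | None stated |
| Failure if no improvement by week 12 (baseline SUN grade 2 or more; or vitreous, retinal or macular disease with more than trace vitreous cells) | Protocol for treatment failure | None stated |
| Failure if no improvement by week 24 (SUN 0 to 1+) | Same | None stated; coincides with the endpoint visit |
| Patient dropped for failure before the tapering phase, or for a second prednisone escalation | Same | None stated |
| No worsening and no additional therapy | Section 5 | Part of the endpoint, but requires only stability |

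The first four rules would identify many patients with unchanged inflammation, but none is linked to non-response in Section 5. They also do not define improvement, and the only definition, in Section 4, can be met by the taper itself. As written, one patient could be both a treatment failure and a responder. These passages must be reconciled.

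**3. Illustration of size.** Assume the drug has no effect, 20% respond anyway, and a fraction f of the other 80% qualify by taper alone. The value of f is not in the documents; the range is an assumption. The no-effect response rate is then

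p = 0.20 + 0.80f,

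and the chance of a positive result is P(X ≥ c) = Σ C(20,k) pᵏ(1 − p)²⁰⁻ᵏ for k = c to 20. Of 20 patients, 16 would not otherwise respond, so the expected number of taper-only responders is 16f.

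| f | Expected taper-only responders | p | P(X ≥ 8) | P(X ≥ 9) |
|---|---|---|---|---|
| 0 | 0 | 0.20 | 3.2% | 1.0% |
| 5% | 0.8 | 0.24 | 8.3% | 3.2% |
| 10% | 1.6 | 0.28 | 17.1% | 7.8% |
| 20% | 3.2 | 0.36 | 43.6% | 26.8% |

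The direction does not depend on the cut; the size depends on both the cut and f.

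**The case against.** The strongest reply is that the protocol already guards against this. Drug is stopped at week 4 without improvement, lack of improvement by week 12 or 24 is treatment failure, and failure before the tapering phase removes the patient. That last rule hints that tapering may follow response. The taper is also reversed when inflammation worsens, so completing it partly reflects disease control. Much of this stands: if these rules were scored as non-response and improvement excluded the taper, few patients with unchanged inflammation would be left as responders. The documents say neither.

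Section 3 also gives relief from glucocorticoid toxicity as a reason for the trial. Steroid reduction without worsening is therefore a relevant benefit, which is a good reason to keep the component in the headline endpoint. It is still a different claim from reduced inflammation.

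A reader might go further than the documents allow in two ways.

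- **That patients become responders simply by following the schedule.** The schedule's doses, start and entry condition are not in the available text, and a figure under Protocol for treatment failure is not reproduced. It cannot be shown that following the schedule reaches 50% by week 24, or that it starts regardless of response. The visible schedule covers prednisone only. No directed taper of ocular steroids appears, and eligibility does not require prednisone, so the scheduled route applies to an unknown subset.
- **That the 20% null rate excludes directed tapering.** That rate is described as spontaneous, but it refers to a composite that includes taper. The text does not say whether a directed taper is allowed for.

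**Conclusion.** The point holds in a limited form. A taper of at least 50% suffices alone, the protocol refers to its own tapering schedule, and failures and dropped patients are not tied to non-response. A positive primary result therefore need not support the stated hypothesis.

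The size is unknown. The range of 8.3% to 43.6% at the 8-of-20 cut, or 3.2% to 26.8% at 9 of 20, rests on assumed values of f from 5% to 20%, no drug effect, and a 20% rate that makes no allowance for directed taper. It shows how sensitive a 20-patient single-arm test is to a few taper-only responders. It does not estimate this trial's error rate, and the documents do not support a claim that the result would come mainly from the schedule.

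**What to change.** Keep the primary endpoint as the headline and add to the analysis text:

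1. The same test on the composite with the taper removed as a qualifying component (visual acuity, inflammation and macular edema remain). Leave the no-worsening and no-additional-therapy conditions unchanged. Responders here are then a subset of headline responders, so if 20% is right for the full composite, testing against it is no more lenient.
2. The number of responders whose only qualifying component was taper.
3. A statement that any conclusion about reduced ocular inflammation rests on analysis 1.
4. A statement that patients who met a treatment-failure rule or were dropped before week 24 count as non-responders in both analyses. The failure rules, the Section 4 definition of improvement and Section 5 need reconciling so that this count is unambiguous.

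Counting taper within the primary endpoint only when inflammation is also controlled would be a real trade-off, because steroid sparing is part of the rationale; it is not needed here.

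The cost is a few lines of text and one table. Eye examination, visual acuity, optical coherence tomography and the medication list are already scheduled at week 24, so no new data are needed. The downside is that both response rates may be lower than the headline rate as now defined, with correspondingly less power in 20 patients.
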